### **10.1 Handling of the BLQ and the No Reportable Concentration Values**

All concentration values below the lower limit of quantitation (BLQ) and samples with no reportable value occurring prior to dosing (on Day 1 only) will be replaced by “0”. For tabulation, graphical representation and calculation purposes, all samples with no reportable value observed after administration of the first dosing will be set to missing.

## 10.2 Handling of the Difference between the Scheduled and the Actual Sampling Times

The actual clock time for dosing and the actual clock time for each collection time for the PK samples will be recorded using the electronic data capture. For all sampling times, the actual sampling times will be calculated as the difference between the sample collection actual clock time and the actual clock time of dosing. The actual post-dose sampling times expressed in hours and rounded off to three decimal digits will be presented, except for pre-dose samples occurring prior to dosing, which will always be reported as zero (0.000), regardless of the time difference. A listing of the actual times will be provided for PK samples. However, the scheduled sampling times will be used for calculation of the PK parameters. In the PK section of the report, scheduled sampling times will be presented in concentration tables, mean graphs, and the individual graphs.

## 10.3 Pharmacokinetic Concentration and Parameters

A total of 55 PK blood samples will be taken from subjects in the oral groups (Treatments “A” and “B”) for the evaluation of the leuprolide serum concentrations at Dosing period Day 1 and Day 28 immediately prior to dosing (0 time), and at 0.500, 1.00, 1.50, 2.00, 2.50, 3.00, 3.50, 4.00, 4.50, 5.00, 6.00, 7.00, 8.00, 10.0, 12.0, 13.0, 14.0, 15.0, 16.0, 17.0, 18.0, 20.0, and 24.0 hours following oral dosing and also in morning prior to dosing on Days 8, 15, and 22. There will be samples taken in Post-dosing Evaluation Period Day 7, 14, 21 and 28.

A total of 16 PK blood samples will be taken from subjects in the Lupron group (Treatment “C”) for the evaluation of the leuprolide serum concentrations at Dosing period Day 1 prior to dosing (0 time), at 0.500, 1.00, 2.00, 6.00, 12.0, 18.0, and 24.0 hours post-dosing, Day 8, 15, 22 and Post-dosing Evaluation Period Day 1, 7, 14, 21 and 28.

Subjects enrolled to the third oral dose (Treatment “D”) will have a very few PK samples: just prior to the first study drug administration and immediately prior to the first dose of the day on Treatment Days 8, 15, 22, and in the morning of Day 29. The PK samples will also be taken in Post-dosing Evaluation Period Day 7, 14, 21 and 28.

PK parameters will be calculated using the scheduled sample collection timepoints. For each evaluation period (*i.e.*: Treatment Days 1 and 28 for the oral groups and day 1 for the Lupron Depot group), where applicable, serum concentrations from leuprolide acetate will be used to calculate the following parameters by standard non-compartmental methods: Note: these PK parameters will be calculated for each treatment period for Treatment groups “A”, “B” and “C” only.

$AUC_{0-24}$  Area under the drug concentration versus time curve calculated using the linear trapezoidal method from 0 hours to 24 hours. In the case where the 24 hours concentration value is missing,  $AUC_{0-24}$  will not be calculated.

$AUC_{0-t}$  Area under the drug concentration versus time curve calculated using the linear

	trapezoidal method from 0 hours to t, where t is the time of the last available observation ( $C_t$ )
$AUC_{0-inf}$	Area under the drug concentration versus time curve from 0 hours to infinity, $AUC_{0-inf} = AUC_{0-t} + C_t/K_{el}$
$C_{max}$	Maximum concentration level
$C_{ss\_oral}$	Steady state concentration level calculated for oral tablets at the end of the fourth treatment week (Treatment Days 28-29) as the 24-hour AUCs divided by the duration of the dosing interval i.e. 24 hours.
$C_{ss\_im}$	Steady state concentration level calculated for IM injection at the fourth treatment week (a mean of leuprolide levels on Days 22 and 29).
$T_{max}$	Time to maximum concentration level
$T_{1/2\ el}$	Terminal half-life calculated as $\ln(2)/K_{el}$
$K_{el}$	The apparent elimination rate constant, calculated by linear regression of log concentration vs time during the elimination phase

To derive the PK parameters, the serum concentrations below limit of quantification in early timepoints will be treated as zero and serum levels below limit of quantification appearing in the elimination phase will be omitted from the calculations of  $K_{el}$ .

Some PK parameters may not be calculated for all or some subjects, at the discretion of the inVentiv pharmacokineticist, if the concentration data is not deemed to be amenable to evaluation. Explanations for PK parameters that could not be estimated will be provided in the CSR report.

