### 12.2 Pharmacokinetic Parameters and Analyses

The following PK parameters will be calculated from the individual serum drug concentration versus time profiles for each subject from Treatment groups "A", "B" and "C" and for each treatment period:

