**Table 1 Description of the Pharmacokinetic Parameters**

Parameter	Description
Cmax	Maximum concentration level
Tmax	Time to maximum concentration level
AUC0-24	Area under the drug concentration versus time curve calculated using the linear trapezoidal method from 0 hours to 24 hours
AUC0-t	Area under the drug concentration versus time curve calculated using the linear trapezoidal method from 0 hours to t, where t is the time of the last available observation (C t )
AUC0-inf	Area under the drug concentration versus time curve from 0 hours to infinity, $AUC_{0-inf} = AUC_{0-t} + C_t/K_{el}$
Css_oral	Steady state concentration level calculated for oral tablets at the end of the fourth treatment week (Treatment Days 28-29) as the 24-hour AUCs divided by the duration of the dosing interval.
Css_im	Steady state concentration level calculated for IM injection at the fourth treatment week (a mean of leuprolide levels on Days 22 and 29).

Kel	The apparent elimination rate constant, calculated by linear regression of log concentration vs time during the elimination phase
T1/2	Terminal half-life calculated as $\ln(2)/K_{el}$

PK parameters will be derived using a non-compartmental PK model. Scheduled sampling time points will be used for the calculations. To derive the PK parameters, the serum concentrations below limit of quantification in early timepoints will be treated as zero and serum levels below limit of quantification appearing in the elimination phase will be omitted from the calculations of Kel.

The summaries will be provided for all PK parameters with steady-state concentration levels (Css) considered as most important. No formal statistical between-treatment comparisons will be conducted. PK parameters will be graphed by treatment group for each evaluation period.

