#### **Pharmacokinetics**

##### **Absorption**

A single dose of LUPRON DEPOT 3.75 mg was administered by intramuscular injection to healthy female volunteers. The absorption of leuprolide was characterized by an initial increase in plasma concentration, with peak concentration ranging from 4.6 to 10.2 ng/mL at four hours postdosing. However, intact leuprolide and an inactive metabolite could not be distinguished by the assay used in the study. Following the initial rise, leuprolide concentrations started to plateau within two days after dosing and remained relatively stable for about four to five weeks with plasma concentrations of about 0.30 ng/mL.

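### AUC0-inf, Kel and half-life for Lupron Depot are planned from a 24-hour profile, so they would describe the initial burst and not the month-long depot

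*SAP*

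**What the plan says.** SAP 10.3 gives the evaluation periods for the PK parameters as "Treatment Days 1 and 28 for the oral groups and day 1 for the Lupron Depot group". Its list includes AUC0-inf (defined as AUC0-t + Ct/Kel), Kel and terminal half-life, and it adds that "these PK parameters will be calculated for each treatment period for Treatment groups “A”, “B” and “C” only". Protocol Section 12.2, which covers the depot group along with both 4-mg oral groups, opens its list with "The following PK parameters will be calculated from the individual serum drug concentration versus time profiles for each subject from Treatment groups". Table 1 there defines Kel as "The apparent elimination rate constant, calculated by linear regression of log concentration vs time during the elimination phase". The protocol synopsis and Section 7.1 also tie the depot's PK parameters to Day 1; the synopsis names AUC0-inf among them.

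The depot's Day 1 samples are predose and "at 0.500, 1.00, 2.00, 6.00, 12.0, 18.0, and 24.0 hours post-dosing". Later samples are on "Day 8, 15, 22 and Post-dosing Evaluation Period Day 1, 7, 14, 21 and 28".

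The label reproduced in protocol Appendix D (Pharmacokinetics, Absorption) reports a peak of 4.6 to 10.2 ng/mL at four hours and a plateau starting within two days. Concentrations then "remained relatively stable for about four to five weeks with plasma concentrations of about 0.30 ng/mL". It also says that the assay could not tell intact leuprolide from an inactive metabolite.

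The SAP makes Css_im, the mean of the Day 22 and Day 29 levels, the primary PK endpoint for the Lupron group. It plans summaries of leuprolide at every intermediate and follow-up visit, and no formal comparison between treatments.

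**The concern.** Ct/Kel is a valid tail only if the fitted slope is the terminal slope. For this depot, the first 24 hours fall between the burst and the start of the plateau, so the regression picks up the post-burst decline. Kel and half-life would then be reported under names that do not fit what was measured, and AUC0-inf would leave out most of the plateau.

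This matters because comparative PK of the tablets and the depot is a primary objective, and the study is meant to bridge to historical Lupron Depot data. SAP Section 5 lists AUC0-inf, Kel and half-life among the primary parameters, and Section 10.4 promises summaries of all listed PK parameters. A depot half-life of a few hours, or an AUC to infinity smaller than one month's exposure, could be taken at face value.

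**Working it through.** **1. Sampling.** Day 1 gives 8 samples (0, 0.5, 1, 2, 6, 12, 18, 24 h). Days 8, 15 and 22 give 3, and postdosing Days 1, 7, 14, 21 and 28 give 5. 8 + 3 + 5 = 16, which matches the SAP: "A total of 16 PK blood samples will be taken from subjects in the Lupron group". The documents state no depot AUC0-inf, Kel or half-life to reproduce.

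**2. Inputs.** From the label: peak P = 4.6 to 10.2 ng/mL at 4 h (midpoint 7.4), plateau 0.30 ng/mL, and intravenous half-life about 3 h. The rise is taken as linear to 4 h. The shape between 4 h and 48 h is an assumption, taken two ways:

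- Shape A: log-linear from P at 4 h to 0.30 at 48 h, with rate λ = ln(P/0.30)/44.
- Shape B: 0.30 + (P − 0.30) × 2^(−(t − 4)/3).

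**3. 28-day AUC (672 h) of each profile, for P = 7.4.**

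- A: 7.4 × 4/2 + (7.4 − 0.30)/0.0729 + 0.30 × 624 = 14.8 + 97.5 + 187.2 = 299.5 ng·h/mL, using unrounded λ.
- B: 14.8 + 0.30 × 668 + 7.1 × 3/ln 2 = 14.8 + 200.4 + 30.7 = 245.9 ng·h/mL.

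The plateau from Day 2 to Day 28 alone is 0.30 × 24 × 26 = 187 ng·h/mL.

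**4. Planned calculation.** Linear trapezoid to 24 h at the scheduled times, Kel from the last three points (an assumed choice; the plan gives no rule), then AUC0-24 + C24/Kel. For A with P = 7.4: 89.1 + 1.724/0.0729 = 112.7, and 112.7/299.5 = 0.38.

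| Shape | Peak | AUC0-24 | C24 | Kel (/h) | Half-life (h) | Planned AUC0-inf | 28-day AUC | Ratio |
|---|---|---|---|---|---|---|---|---|
| A | 4.6 | 59.6 | 1.330 | 0.0620 | 11.2 | 81.0 | 265.7 | 0.30 |
| A | 7.4 | 89.1 | 1.724 | 0.0729 | 9.5 | 112.7 | 299.5 | 0.38 |
| A | 10.2 | 117.1 | 2.053 | 0.0801 | 8.6 | 142.7 | 331.1 | 0.43 |
| B | 4.6 | 31.7 | 0.342 | 0.0874 | 7.9 | 35.6 | 228.2 | 0.16 |
| B | 7.4 | 48.1 | 0.370 | 0.1120 | 6.2 | 51.4 | 245.9 | 0.21 |
| B | 10.2 | 64.5 | 0.397 | 0.1286 | 5.4 | 67.6 | 263.6 | 0.26 |

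With four points, A is unchanged. B gives half-lives of 5.7, 4.9 and 4.4 h and ratios of 0.15, 0.21 and 0.25. The overall range is 15% to 43%, with half-life 4.4 to 11.2 h. Css_im on every profile is (0.30 + 0.30)/2 = 0.30 ng/mL.

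**5. Peak.** The label's 4 h peak lies between the 2 h and 6 h samples. The highest scheduled value (6 h) is 64% to 88% of P in these profiles.

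**6. A 28-day AUC from scheduled samples** (Day 1 profile plus Days 8, 15, 22, 29, linear trapezoid). A gives 328.1, 386.0 and 437.7 against 265.7, 299.5 and 331.1, which is 23% to 32% high. B gives 229.1, 247.5 and 265.9 against 228.2, 245.9 and 263.6, which is 0% to 1% high. The excess comes from having no sample between 24 h and Day 8.

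**7. Direction in an oral-versus-depot ratio.** Protocol 7.1.1 puts A and B at about 6% and 12% of the 1-mg subcutaneous exposure, and Section 5 gives that exposure as 163021 h·pg/mL. Read as 24-hour values (an assumption), these are 9.8 and 19.6 ng·h/mL per day, or about 274 and 548 over 28 days.

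- 28-day oral over 28-day depot (228 to 331): A 0.83 to 1.20, B 1.65 to 2.40.
- One-day oral over planned depot AUC0-inf (34.5 to 142.7): A 0.07 to 0.28, B 0.14 to 0.57.
- 28-day oral over planned depot AUC0-inf: A 1.9 to 7.9, B 3.8 to 15.9.

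**The case against.** The strongest reply is that the plan does not rest on these parameters. Css_im is the ranked depot endpoint and uses neither Kel nor AUC0-inf. The weekly summaries show the plateau directly, and no formal comparison is planned. SAP Section 5 lists every PK parameter as primary, so that label carries little weight. All of this stands, and it is why the point is minor.

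The second reply is that the SAP has safeguards. It qualifies the calculations as applying where applicable, confines Kel to the elimination phase, lists the limits of the Kel window among its parameters, and lets the pharmacokineticist withhold parameters with an explanation in the study report. This softens the defect without removing it. The discretion is general, and nothing excludes these parameters for C. The data might also look acceptable: with three points, the fits above have r-squared of 0.95 to 1.00, and only 5% to 26% of AUC0-inf is extrapolated.

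The last available observation in the definition of AUC0-t could be read as a later visit, but the Day 1 wording points to 24 hours.

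**Conclusion.** The plan calls for three depot parameters that a Day 1 profile cannot support. With the label's figures, AUC0-inf would be about 15% to 43% of the 28-day AUC, and the half-life about 4 to 11 hours. The size rests on the assumed decline between 4 and 48 hours, on the choice of points for Kel, and on label concentrations from an assay that did not separate an inactive metabolite. If the fitted points happened to be nearly flat, Kel would be close to zero and AUC0-inf unstable rather than low.

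A reader might infer two stronger things, and the documents support neither. One is that the depot's exposure as a whole would be understated; Css_im and the by-visit levels are untouched. The other is that the tablets would look closer to Lupron than they are. Step 7 shows that the oral-to-depot ratio moves down or up according to which oral AUC is set beside the depot value, and the plan specifies no such ratio.

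Severity: minor.

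**What to change.** State in SAP 10.3, and record in SAP Section 4 as a change from the protocol, that AUC0-inf, Kel and half-life are not reported for Treatment C from Day 1. Keep AUC0-24, Cmax and Tmax for C, labelled as measures of the initial burst. Footnote that no sample is scheduled between 2 h and 6 h, where the label places the peak.

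If a total depot exposure is wanted, add AUC0-28d as a descriptive parameter from the Day 1 profile and the Day 8, 15, 22 and 29 samples. Footnote that the gap between 24 h and Day 8 can make linear interpolation about 0% to 32% high under the shapes tried here.

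The cost is a few lines of SAP text and, optionally, one derived parameter. No new samples are needed.

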**Date**

4. PROTOCOL SYNOPSIS

Title of Study	A randomized, open-label, parallel-group, active-control study to evaluate the pharmacokinetic (PK) and pharmacodynamic (PD) profiles of three doses of Leuprolide Oral Tablets (Ovarest™) in comparison to an intramuscular (IM) dose of leuprolide acetate (Lupron Depot 3.75 mg) in healthy female volunteers
Protocol Number	LOPDT-ENDO-01
Phase	2a
Number of Study Centers	One or two sites, Phase I clinical unit(s) in the North America (US and/or Canada)
Investigational Product, Dosage, and Route of Administration	
Leuprolide Oral Tablets (Ovarest™) utilizing Enteris' Oral Peptide Delivery Technology. The Ovarest™ dosing regimens are selected based upon the results of the PK study LOPD-PH1-01.
 
The Ovarest™ dosing regimens are:  Treatment "A": Leuprolide Oral Tablet (Ovarest™), 4 mg, administered daily (qd) for 28 consecutive days  Treatment "B": Leuprolide Oral Tablet (Ovarest™), 4 mg, administered twice daily (bid), 12 hours apart for 28 consecutive days  Treatment "D": Leuprolide Oral Tablet (Ovarest™), 10 mg, administered twice daily (bid), 12 hours apart for 28 consecutive days

Control Drug (Reference Product)	Treatment C : Leuprolide Acetate intramuscular (IM) injection (Lupron Depot 3.75 mg) administered for one month of therapy
Study Design	Randomized, Open-Label, Parallel-Group, Active-Control Study for Treatment "A", Treatment "B" and "Treatment "C". Treatment "D" will be evaluated in a Non-Randomized, Open-Label, Single-Group Study design setting.
Study Objectives	
The objectives are to determine the safety, PK profile, and PD effects of the three doses of Ovarest™ in healthy female volunteers in comparison to a marketed dose of leuprolide acetate administered IM (Lupron Depot 3.75 mg). Note: For the third Ovarest dose (Treatment "D"), a complete PK profile will not be evaluated.
 
This trial will serve as a bridging PK/PD study between the 4 mg Leuprolide Oral Tablet administered over 28 days as qd or bid regimens, the 10 mg Leuprolide Oral Tablet administered over 28 days as a bid regimen, and a marketed IM injection of leuprolide acetate (Lupron Depot 3.75 mg) designed for one month of therapy. This trial will also be a bridging study to historical

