## 7. STUDY DESIGN

### 7.1 Overall Study Design and Plan – Description

This study will evaluate the safety, PK profile and PD effects of the three Ovarest™ dosing regimens: Leuprolide Oral Tablet, 4 mg, administered qd for 28 consecutive days (Treatment “A”), Leuprolide Oral Tablet, 4 mg, administered bid for 28 consecutive days (Treatment “B”), and Leuprolide Oral Tablet, 10 mg, administered bid for 28 consecutive days (Treatment “D”), in comparison to leuprolide acetate administered IM, Lupron Depot 3.75 mg (Treatment “C”).

The study was originally designed as a randomized, open-label, parallel-group active-control trial. Up to thirty-two (32) subjects (12 subjects in each Ovarest™ treatment group and 8 subjects in the Lupron Depot group) were to be randomly assigned to the study drug in a Treatment “A”:Treatment“B”:Treatment“C” ratio of 3:3:2. The randomization schedule was to be balanced by using permuted blocks. The randomization schedule could be further stratified by the study site, if necessary.

[figure not shown]
Twenty-three subjects were initially enrolled in this study (9 subjects in each of Ovarest treatment groups and 5 subjects in the Lupron Depot group). At the time of the current protocol Amendment, all initially enrolled subjects had completed the study, except for one subject who was withdrawn on post-dose Day 1 (due to vomiting). After interim PK and safety evaluations, it was decided not to enroll any new subjects in Treatment Groups “A”, “B” and “C”. Instead, up to twelve (12) subjects will be enrolled in a new Treatment Group D” (Leuprolide Oral Tablet, Ovarest, 10 mg, administered twice daily (bid), 12 hours apart for 28 consecutive days).

The study consists of two major periods: approximately one month of dosing (either 28 consecutive days of daily oral dosing, or a single IM injection on Treatment Day 1) and approximately 1 month (28

days) of postdosing PK/PD evaluations. The total study duration from screening to the final study visit will be up to approximately 3.5 months.

Study design schematic is displayed in Figure 1 below. A detailed “Times and Events Schedule” is presented in APPENDIX B.

Figure 1 Study Design Schematic

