empty stomach. Note: On an empty stomach means that the oral doses are administered at least 2 hours before and at least 2 hours after the meal. For clarity, all oral doses have to be taken on an empty stomach except for the morning doses of Days 1 and 28, for which the fasting period is -10h to +4h. Subjects randomized to the two oral doses (Treatments “A” and “B”) will have twenty-four (24) serial serum samples drawn on Treatment Days 1 and 28 immediately prior to dosing (0 time), and at 0.5, 1, 1.5, 2, 2.5, 3, 3.5, 4, 4.5, 5, 6, 7, 8, 10, 12, 13, 14, 15, 16, 17, 18, 20, and 24 hours following oral dosing. For Treatment “B”, the PK blood draws will be drawn for the morning dose. For the IM injection (Treatment “C”), serial serum samples will also be drawn on Treatment Day 1, prior to dosing (0 time), at 0.5, 1, 2, 6, 12, 18, and 24 hours postdosing. Blood samples for the IM injection will also be taken in the morning on Postdosing Day 1. Additional blood samples for all subjects will be taken in the morning (in the oral groups, just prior to dosing) on Treatment Days 8, 15, and 22. Samples will be appropriately stored until they can be assayed for leuprolide and hormonal levels. Serum concentrations of LH, FSH, E2, and progesterone will be measured (immediately prior to dosing) on Treatment Days 1, 8, 15, 22, and in the morning of Day 29.

Subjects enrolled to the third oral dose (Treatment “D”) will have a dosing initiation visit scheduled 5-9 days before the anticipated start of their next menstrual cycle, based on their self-reported menstrual cycle length and the day the current menstrual cycle began. During the visit, just prior to the first dosing, baseline blood samples will be taken for leuprolide and hormonal levels. The same blood draws will be performed immediately prior to the first dose of the day on Treatment Days 8, 15, 22, and in the morning of Day 29.

On Day 29, after the 24-hour blood draws in the oral groups (Treatments “A” and “B”) and after the PK/PD blood draws in the Treatment “D” and the IM injection group (Treatment “C”), physical, gynecological, and safety laboratory evaluations will be performed.

Note: throughout the text, Treatment Day 29 may be used interchangeably with Postdosing Day 1.

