**Treatment Day 1 – Treatments “A”, “B”, and “C”**

- Verify no change in subject’s health status before dosing.
- Assign randomization number.
- Obtain baseline PK blood sample immediately (within 10 minutes) prior to dosing.
- Obtain baseline PD blood sample (LH, FSH, E2, and progesterone) immediately (within 30 minutes) prior to dosing.
- Do not allow any food or liquid during the fasting period, except water, which is permitted up until 1 hour prior to study drug administration.
- Administer study drug in the morning according to the randomization schedule. Oral tablets will be administered with 240 mL of water. Perform mouth check following oral tablet dosing to ensure compliance.
- Subjects will remain seated or semireclined and will be required to avoid lying down or sleeping (unless medically necessary or procedurally required) for the first 1 hour after drug administration.
- Obtain serial blood samples for the PK evaluations at 0.5, 1, 1.5, 2, 2.5, 3, 3.5, 4, 4.5, 5, 6, 7, 8, 10, 12, 13, 14, and 15 hours following single oral dosing in Treatment group “A” or the first oral dosing in Treatment group “B” (16, 17, 18, 20, and 24 hour samples to be obtained on Treatment Day 2). Note: A 12-hour sample in Treatment group “B” will be obtained within 10 minutes before the second oral dose.
- Obtain serial blood samples for the PK evaluations at 0.5, 1, 2, 6, and 12 hours following an IM injection (Treatment “C”) (18 and 24 hour samples to be obtained on Treatment Day 2).
- Assess body weight and vital signs (temperature, pulse rate, respiratory rate, systolic and diastolic blood pressure) predose (within 2 hours prior to dosing). Note: The vital signs will be assessed prior to the single oral dosing in Treatment group “A”, prior to the first oral dosing in Treatment group “B” and prior to the IM injection in Treatment group “C”.
- Record adverse events (AEs) and concomitant medication use.
- The fasting period will be -10h to +4h for Treatment groups “A” and “C.”, and -10h to +4h for the first dose in Treatment group “B”, and -2h to +2h for the second dose in Treatment “B”. All meal times will be recorded and entered into the clinical database.
- Water will not be permitted until 1 hour after dosing.

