## **12.5 Sample Size**

The sample size for this study is not based on the statistical power considerations. This sample size is considered as adequate for a pilot PK/PD “proof-of-concept” study. Since a formal proof of the PK bioequivalence across the treatment arms and/or formal across-treatment statistical comparisons of the PD endpoints are not objectives of this proof-of-concept study, the sample size is not based on the power considerations. With the proposed sample size, we expect reliable estimates of the PK and PD parameters for leuprolide oral tablets and a general validation of related historical data for Lupron Depot therapy. The safety and tolerability assessments of the qd and bid regimens of the 4-mg oral tablet and a bid regimens of the 10-mg oral tablet should also be robust enough to support the dosing selection and instructions in subsequent clinical studies.

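### For bid Treatment B, the SAP takes one Cmax and one Tmax from a 24-hour profile containing two doses, so neither is like-for-like with qd Treatment A

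*SAP*

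**What the plan says.** Treatments A and B use the same 4 mg tablet, once daily in A and, in B, "administered twice daily (bid), 12 hours apart for 28 consecutive days" (Protocol synopsis). Both groups have 24 serial samples over 0–24 h on Days 1 and 28. In B the Day 1 12-h sample "will be obtained within 10 minutes before the second oral dose" (Protocol 7.2), and Day 28 follows the same pattern, so the second dose lies inside both profiles.

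SAP 10.3 calculates one set of parameters per evaluation period, Days 1 and 28 for the oral groups. Cmax is "Maximum concentration level" and Tmax is "Time to maximum concentration level". Neither definition has a time window or a reference dose. For Css_oral the SAP sets the interval at 24 h for both oral groups.

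Two further passages bear on this. Protocol 7.1 says that for B "the PK blood draws will be drawn for the morning dose". Protocol 7.2 gives B's two doses different fasting windows: 10 h before to 4 h after the first dose, but only "2h to +2h for the second dose in Treatment" B.

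**The concern.** A's Cmax comes from one dose. B's is the higher of two, and the higher of two variable peaks exceeds a single peak on average even when every dose is absorbed identically. A reader of the summary table could take the difference for accumulation or for better absorption under bid dosing.

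Tmax has a different problem. A subject whose higher peak follows the morning dose has a Tmax of about t; one whose higher peak follows the evening dose has about 12 + t. Summarising these together gives a figure that describes neither dose.

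At stake is the description of per-dose absorption under the two regimens. SAP 5 lists Cmax and Tmax among the primary parameters. Treatment D has no serial profile, so A against B is the only contrast of full oral profiles in the trial.

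**Working it through.** **Inputs from the documents.** B is dosed at 0 and 12 h. The enrolled numbers were "9 subjects in each of Ovarest treatment groups and 5 subjects in the Lupron Depot group" (Protocol 7.1). The protocol's 55 PK samples reproduce: 24 times × 2 days + Days 8, 15 and 22 + 4 follow-up visits = 48 + 3 + 4 = 55. Of the 24 times, one is pre-dose, 15 run from 0.5 to 12 h and 8 from 13 to 24 h. Protocol 7.1.1 describes a peak-and-trough pattern. The label in Appendix D gives an IV half-life of about 3 h, so about 2^(−12/3) = 6% of a level remains after 12 h and the peaks are largely separate.

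**Not in the documents, so assumed.** Within-subject dose-to-dose CV of peak height (30% to 100%), and the exposure from dose 2 relative to dose 1 (1, 0.75 or 0.5).

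**Direction for Cmax.** In any subject, the maximum over 0–24 h cannot be below the maximum over 0–12 h. B's Cmax can only move up.

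**Size, equivalent doses, closed form.** For two independent log-normal peaks with the same distribution, E[max]/E[single] = 2Φ(s/√2), where s = √ln(1 + CV²). A factor common to both of a subject's peaks cancels.

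| CV | s | Ratio of means |
|---|---|---|
| 30% | 0.294 | 1.16 |
| 50% | 0.472 | 1.26 |
| 70% | 0.631 | 1.34 |
| 100% | 0.833 | 1.44 |

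**Size, simulated on the protocol's sampling times.** One-compartment oral model, 40,000 subjects, dose 2 at 12 h, CV 30%, 50% and 100%, half-life 1.5 or 3 h, median absorption rate 1/h, lag 0 to 1 h. No carry-over from earlier days was modelled.

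| Dose 2 relative to dose 1 | Mean Cmax, 24 h against single dose | Subjects peaking after dose 2 | Mean Tmax | Chance that all 9 peak after the same dose |
|---|---|---|---|---|
| 1 | 1.18–1.46 | 50–57% | 7.9–9.2 h | below 1% |
| 0.75 | 1.06–1.29 | 27–43% | 5.1–7.6 h | 1–6% |
| 0.5 | 1.01–1.15 | 7–31% | 2.8–6.1 h | 4–54% |

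A's mean Tmax in the same runs was 2.0–2.5 h. With equivalent doses, no simulated subject had a Tmax within 1.5 h of B's mean. Restricting B to 0–12 h returned the Cmax ratio to 1.00 and Tmax to A's value in every scenario.

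**Whether the median rescues Tmax.** Take t = 2 h and nine subjects, k of whom peak after dose 2. The mean is 2 + 12k/9: 7.3 h for k = 4 and 8.7 h for k = 5. The median is the fifth ordered value: about 2 h for k = 4 and about 14 h for k = 5. One subject moves it by 12 h.

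**The case against.** The case for leaving the text alone is substantial.

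- **A 24-h Cmax is legitimate.** It is the highest level reached on a day of bid dosing, which is a proper description of the regimen. This stands: calling B's value wrong, or simply inflated, would go too far. The fault is that the text does not distinguish daily peak from per-dose peak.
- **Dose-proportionality is not harmed.** A reader might infer damage to that primary objective. The documents do not support this. A and B both take 4 mg per administration, so their per-dose comparison is 4 mg against 4 mg. D, the only other strength, has no Cmax or Tmax. For these regimens the relevant measure is daily exposure, through AUC0-24 and Css over 24 h.
- **The stakes are limited.** SAP 5 places every PK parameter under the primary heading, so that label carries little weight. SAP 10.4 names Css_oral as most important for the oral groups and plans no formal between-treatment comparison. Protocol 12.5 adds that "The sample size for this study is not based on the statistical power considerations". All of this stands.
- **The problem would be visible.** Individual and mean curves are planned, and Protocol 12.1 lists median, minimum and maximum. A Tmax range from about 2 to 14 h would alert a careful reader. But it does not supply the per-dose values, and the median is unstable, as shown above.
- **Protocol 7.1 ties the draws to the morning dose.** This gives grounds for a 0–12 h reading, but the sampling continues through the second dose and nothing limits the parameter window. The 24-h window is the plain reading of one parameter set per evaluation period; it is not written out for Cmax or Tmax.
- **Equivalent doses are a favourable case.** The fasting windows differ, and sampling after dose 2 is sparser, with nothing at half an hour and hourly draws at first. Both points stand, which is why the lower rows of the table matter.

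**Conclusion.** The point holds as a gap in the definition of Cmax and Tmax for B. That B's 24-h Cmax is at least its single-dose Cmax is certain. The size is not: about 16–46% on the mean if the doses are equivalent (closed form and simulation together), 6–29% at 75% relative exposure and 1–15% at 50%, all on an assumed dose-to-dose CV of 30% to 100%.

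The Tmax effect is conditional. A reader might infer that B's mean Tmax must fall between the peaks, but that needs at least one subject peaking after each dose. This is very likely with equivalent doses and much less sure if dose 2 peaks are far lower.

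The consequence is confined to descriptive Cmax and Tmax summaries and the per-dose comparison of A with B. AUC0-24 and Css_oral are unaffected. The change is worth making because a Tmax pooled across two doses has no clear meaning and the remedy uses data already collected.

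**What to change.** In SAP 10.3, for Treatment B on Days 1 and 28:

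- Derive Cmax and Tmax separately for 0–12 h and 12–24 h, with Tmax counted from the dose that starts each interval. Treat the 12-h sample as the end of the first interval and the pre-dose value of the second.
- Use the 0–12 h values for the comparison with A.
- Report the 24-h maximum separately, labelled as the daily peak of the regimen.
- Summarise Tmax by median and range.
- Keep AUC0-24 and Css_oral over 24 h.

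The cost is a few lines of SAP text and a second set of partial-interval parameters; no new samples are needed. Two limits should be stated with the results. The 12–24 h values rest on sparser sampling and a different fasting window. On Day 28, B's 0–12 h interval also carries some drug from the previous evening's dose, about 6% of the level 12 h earlier if the label's IV half-life applies.
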